How does task loading in a PICU environment impact on clinician situational awareness and awareness of the passage of time?

NCT number: ID not yet assigned

Date: 1 Dec 2021

STUDY INVESTIGATORS

- Principal Investigator (A): [name]
 - Email: [contact]
- Principal Investigator (B): [name]
 - Email: [contact]
- Principal Investigator (C): [name]
 - Email: [contact]

1. PICU, Great Ormond Street Hospital, London, UK
2. Attention & Cognitive Control Group, University College London

INTRODUCTION

There is little published literature on the subject of clinician perception of trends in patient observations on PICUs (Paediatric Intensive Care Units) and how this situational awareness is impacted on by clinical tasks. Human factors training cautions against the loss of situational awareness and time perception but there is no supporting observational data in the IC (Paediatric Intensive Care) setting.

Perceptual loading theory hypothesises that, under low load situations, awareness extends to environmental features not directly related to the task at hand. However in high load situations awareness is restricted to the object of focused attention. Individuals experience different load from a given task depending on their skills and experience.

Our pilot project intends to examine how clinician perception is affected by task loading. In our protocol two tasks are undertaken. The administrative task involves requesting a list of investigations from a clinical guideline. The technical task is the uncomplicated insertion of a central venous catheter (CVC) into a simulated vein. In each case we will record proxies for perception: awareness of the passage of time, the time point at which monitoring changes are noted and retrospective recall of observation trends. Our protocol was designed with psychology input from [name], group leader of the UCL Attention & Cognitive Control laboratory.

Passage of time is measured by the participant pressing a foot pedal linked to timing software at every perceived 10 second interval of elapsed time. A retrospective estimate of total elapsed time will also be recorded. After the second task, immediate verbal questions are asked followed by a written questionnaire which contains questions targeting the participant's awareness of monitoring changes.

Analysis will involve paired t testing of the timing interval and observation trend data to see if task loading significantly impacts accuracy.

BACKGROUND

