Participants will be recruited through convenience sampling of those working or training on the ICUs on days when it is possible to run the tasks. Individuals will not be recruited more than once.

Each participant will be given a numeric study ID and parameters recorded against this including:

- Job title- Consultant/fellow
- Gender- Male/female/prefer not to say
- Age- 21-30/31-40/41-50/51-60/61+
- Number of CVCs that they have previously inserted - <10, 10-50, >50).
- Time since last simulation training- 1 week/ 2-4 weeks/ 1-2 months / 3-6 months / 7-12 months / 1-2 years / >3 years

STUDY OUTCOMES

Primary Outcomes

Mean and standard deviation (accuracy) of time intervals measured.

Accuracy of retrospective recall of trends in monitored observations.

Secondary Outcomes

Impact of experience on time perception and monitoring changes.

STUDY PROCEDURES

Recruitment of participants

Participants will be provided with the information sheet appended and given the opportunity to ask any questions before consenting to the study. They will be asked to sign the appended consent form. Their consent forms will be in no way linked to the data collected such that participants could be identified from their data.

Randomisation

Block randomisation will be used to ensure even distribution of individuals at each grade of experience between the allocation groups. A block size of 4 will be used with 2 strata (grade= Consultant, Other). The randomisation list was determined by an online randomisation service ^[27]. The list generated is included as an appendix.

Two parts of the experimental process are randomised.

The first is the order in which the administrative and technical tasks are performed- this is randomised to remove the impact of primacy-recency impacts as well as task training through more practice with the timing apparatus.

The second is the scenario displayed on the monitor. As we are asking participants to identify a trend, randomisation to an increasing or decreasing trend reduces the likelihood of guessing the correct answer.

The study cannot be blinded at the time of data capture given the significant obvious differences between the tasks.

Study procedure

Structure

The overall structure is outlined below with further detail on each section provided in the following section.

Section order	Comment
Consent and discussion	To ensure valid consent and answer queries

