Randomisation	Randomisation of task order and monitor trend scenario: increasing/decreasing
Timing control task	To assess baseline time perception for each participant
Break	To reset and brief the participant for the first task
First task	Administrative or technical task depending on randomisation

Monitor scenario in first task	The parameters do not change aside from a brief desaturation at 30 seconds into the task, to orient participants to the monitor within the task
Break	To reset and brief the participant for the second task
Second task	Administrative or technical task depending on randomisation
Monitor scenario in second task	There is a desaturation at 30 seconds as before to orient participants to the monitor within the task. The blood pressure then either falls or rises, depending on the randomisation, settling at the final value at 4 minutes. The change in blood pressure only occurs in the second task so as to allow immediate review of trend awareness, this is not possible to do after the first task without introducing bias in the second task.
Post task review	To check immediate recall of monitor trends in the second task. Asked immediately to reduce the impact of recall/memory bias on the answers.
Questionnaire	Provides quantification of any trend in parameters noticed.
Debrief	To answer queries and identify any areas of participant support required.

Experimental scenarios:

Each participant will undertake the timing control task first and then both the administrative and technical tasks, the order of these determined by the randomisation table.

1. Timing control

The participant sits and is asked to push a foot pedal every 10 seconds with no reference to external timekeeping. This task continues for 6 minutes.

Participants are instructed: "Please press the foot pedal every 10 seconds, trying to be as accurate as possible. The task will last for several minutes."

After 6 minutes the participant will be asked for the time period they believe has elapsed between the first pedal press and the last.

2. Administrative task:

Request investigations for a new admission

Equipment required:

- PIMS-TS investigations pack
- Computer signed in to the EPIC learning environment for a dummy patient
- Simulated bedside monitor
 - Varies observations over time in line with preset programming determined by the study team
- Foot pedal and data recorder for time logging

Setup

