 - The trend in monitored observations- increasing or decreasing blood pressure in the second task

The following parameters are measured during both tasks:

- Timestamps of foot pedal use by the participant
- Retrospective recall of total elapsed time
- Time to complete task/progress at experiment end
- Question responses

Following completion of the tasks the data collected can be analysed as below.

Time interval analysis:

- Intervals between pedal presses are extracted for each scenario (timing control/administrative/technical tasks)
 - Derive: min/max/mean/interquartile range/standard deviation for each case
- Comparison of the individual’s retrospective perceived elapsed time with actual elapsed time. Reported as percentage error of actual elapsed time.

This will allow the following results to be reported:

- Mean deviation for each individual from their baseline in each of the tasks.
- Change in retrospective perceived elapsed time compared to actual elapsed time.
- Distribution of timing in the control task for each individual.
- Paired t-test comparison to test if there are significant differences in time interval distribution for each individual between control, administrative and technical tasks.
- Overall proportion of participants showing significant deviation from their own baseline in each of the administrative and technical tasks
- Population limits/mean
- Comparison of the mean perceived time interval between subgroups
 - By task order

- By time within task (split into thirds- 2 minutes each)
- By grade
- By number of CVCs previously inserted
- By first 25% vs last 25% of participants

Monitor trend perception analysis:

Each participant will provide question answers from immediately after the second task.

This will allow the following results to be reported:

- Rationale
 - The first question “Did you see anything of note on the monitor” is chosen to highlight inattentive blindness and is asked immediately to avoid any impact from the role of memory or priming from other questions asked.
 - This will be reported as proportion who noted a change
 - The subsequent questions are asked to elicit responses from those who observed the trend but are not sufficiently confident in their recall to report it.
- From the responses the following can be derived:
 - Correct identification of the blood pressure trend- reported as proportion of participants correct

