 - Correct identification of no trends in other parameters - reported as proportion of participants correct
 - Accuracy of magnitude recall
 - The blood pressure either falls or rises between a systolic/diastolic (mean) of 70/48 (55) and 90/50 (65).
 - From the position of the x on the linear blood pressure scales we can derive:
 - The accuracy of the initial and final estimates compared with the actual values- reported for each task as the population mean and standard deviation of the percentage errors compared with the actual value.
 - The accuracy of the magnitude of the change, determined through comparing the difference in the estimated initial and final values compared with the actual 20mmHg systolic/ 10mmHg diastolic change for each task. The population mean and standard deviation of the percentage errors compared with the actual change will be reported for each task.
 - We hypothesised that there would be a priming effect following administration of the questionnaire, with participants more likely to attend to blood pressure trends if the questions were asked prior to the second task. We will therefore only ask the questions after the second task. We can then compare between the subgroups, split by which of the tasks was performed second to examine the impact of task type.
 - i.e the questionnaire analysis will have half the n of the overall study
- For the above we can compare subgroups using Fishers exact test.
 - By task order
 - By grade
 - By number of CVCs previously inserted

- By first 25% vs last 25% of participants

STATISTICAL CONSIDERATIONS AND DATA ANALYSIS

Sample size and statistical power

This is a pilot study and as such we do not expect it to be adequately powered to confirm hypotheses but intend that it should be hypothesis generating.

Statistical methods

The population summary statistics detailed above will be calculated using 'SPSS statistics' software with built-in min/max/mean/IQR/SD calculation.

With assumed normally distributed timing data and each participant completing 2 tasks the distributions will be compared with a paired sample t-test for; control vs administrative, control vs technical and administrative vs technical. For subgroup analysis paired or unpaired sample t-tests will be used as appropriate in each case. For the trend perception outcomes, contingency tables will be created for each subgroup and compared using Fishers exact test.

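### Fisher's exact test is assigned to continuous blood-pressure recall errors with no cut-point, and the Introduction promises paired t-tests on trend data that contain no pairs

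*Combined protocol and SAP*

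**What the plan says.** Study outcomes lists as a primary outcome "Accuracy of retrospective recall of trends in monitored observations". The Monitor trend perception analysis derives two kinds of measure from it.

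- **Binary measures**, reported as proportions: whether a change was noted, whether the direction of the blood pressure trend was right, and whether the other parameters were correctly said to show no trend.
- **Magnitude of recall**, from crosses placed on linear pressure scales: the error in the initial value, the final value and the size of the change. For the last of these, "The population mean and standard deviation of the percentage errors compared with the actual change will be reported for each task".

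The list closes with "For the above we can compare subgroups using Fishers exact test". Statistical methods repeats the instruction for trend perception outcomes as a class, using contingency tables, and gives no exception, category or cut-point.

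The Introduction gives a different test: "Analysis will involve paired t testing of the timing interval and observation trend data to see if task loading significantly impacts accuracy". The study structure table, however, says "The change in blood pressure only occurs in the second task so as to allow immediate review of trend awareness", and the trend analysis section says "We will therefore only ask the questions after the second task".

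**The concern.** A percentage error read from a mark on a line is a continuous value. It does not form a contingency table until someone cuts it, and the plan does not say where. An analyst who follows the text literally must choose a cut-point, possibly with the data in view, and discards information in doing so.

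The Introduction adds a second mismatch. A paired test needs two trend observations from the same person, one under each task, and the design gives one. The document therefore names two different tests for the trend data. One does not fit the magnitude component and the other fits none of it.

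The stakes are limited but real. The magnitude errors are part of a primary outcome, and H_B concerns awareness of monitoring trends.

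**Working it through.** The plan states no sample size, alpha, power or effect size for this outcome, so it has no figure of its own to reproduce.

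**Step 1. Match each trend outcome to the test named for it.**

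| Outcome | Scale | Test in the trend and methods sections | Fits? |
|---|---|---|---|
| Noted a change | yes/no | Fisher | yes |
| Correct direction of blood pressure | correct/incorrect | Fisher | yes |
| Correct no-trend in other parameters | correct/incorrect | Fisher | yes |
| Percentage error: initial, final, change | continuous, summarised by mean and SD | Fisher, no cut-point | no |

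**Step 2. Count the pairs.** The pressure drift runs only during the second task. On the answers, the plan says "Each participant will provide question answers from immediately after the second task". Measurement tools used does list question responses among items measured during both tasks, but the trend section explains that asking earlier would prime participants, so that line does not create a pair. Each participant contributes one set of trend answers under one task type. Within-participant pairs: 0. The trend section itself describes the task comparison as one between subgroups defined by which task came second.

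**Step 3. Count the groups.** The randomisation list has 10 administrative-first and 10 technical-first slots in each of the two role strata. That gives 10 + 10 = 20 slots per order, so at most 20 v 20 independent observations if all 40 slots are filled.

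**Step 4. Fisher's test on uncut values.** If all 40 values differ, the 2 x 40 table has C(40,20) = 137,846,528,820 possible allocations, all equally probable. The p-value sums every allocation no more probable than the observed one, which is all of them, so p = 1 whatever the data. Some grouping is therefore unavoidable.

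**Step 5. What a split costs (illustration only).** Assumptions: n = 20 per group, normal errors, two-sided alpha 0.05, standardised difference d.

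Unpaired t-test: df = 2n − 2 = 38, noncentrality = d√(n/2). At d = 0.8 this is 0.8 × √10 = 2.53, and the noncentral t distribution gives power 0.69. Fisher's test was simulated (20,000 runs) after a split at the midpoint between the two group means.

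| d | Unpaired t | Fisher after midpoint split | Difference |
|---|---|---|---|
| 0.5 | 0.34 | 0.14 | 0.20 |
| 0.8 | 0.69 | 0.36 | 0.33 |
| 1.0 | 0.87 | 0.55 | 0.32 |

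The choice of split moves the Fisher figure at d = 0.8 over about 0.36 to 0.40. Mann-Whitney at d = 0.8 has power of about 0.66. With no true difference, Fisher after the midpoint split rejects in about 0.02 of runs, against 0.05 for the t-test.

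**The case against.** Five points can be made for the plan.

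- **Fisher's test is right for most of this outcome.** This stands. The direct measures of trend recall are binary, and the plan compares them between independent groups with a valid exact test.
- **The paired t-test for trend data appears only in an overview sentence.** This also stands. Statistical methods ties the paired test to timing data. A reader might infer that the plan directs a paired analysis of unpaired groups, but the operative section does not; the Introduction sentence is simply wrong and needs correcting.
- **The percentage errors are only to be described, since the plan says they are reported and that subgroups *can* be compared.** This stands in part. The wording is permissive, and a cut chosen after seeing the data is a risk the text leaves open rather than something it plans. But the only comparison offered for these values is Fisher's test.
- **Statistical methods allows paired or unpaired t-tests for subgroups as appropriate.** A generous reader could take this to cover the errors. However, it follows the sentence on timing data, and the next sentence sends trend outcomes to Fisher's test without exception.
- **Magnitude is also asked as a fixed choice of 5, 10, 15, 20 or 25 mmHg.** Those answers do form a contingency table without any cut. That covers the verbal question, not the marks on the line.

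The study is also explicitly a hypothesis-generating pilot. That lowers the stakes, but a pilot analysis still has to be one that can be run as written.

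**Conclusion.** The point holds for the magnitude-recall component of the trend primary outcome: the stated test cannot use the percentage errors without a dichotomisation that the plan does not define. The Introduction separately contradicts the design by promising paired tests where there are no pairs.

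Two stronger conclusions are tempting. A reader might infer that the trend primary outcome has no valid test at all. The documents do not support that, because Fisher's test is valid for its binary measures. A reader might also apply the asymptotic efficiency of a median split, 2/π = 0.637, to 40 people and conclude that about 14 are thrown away (0.363 × 40 = 14.5). The plan specifies no median split, and 40 is the approximate staff pool and the number of list slots, not a stated sample size.

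The size is therefore illustrative: about 0.69 against 0.36 to 0.40 in power at a standardised difference of 0.8. It rests on assumed full recruitment of 20 v 20, normal errors and an assumed effect. Recruitment is by convenience, and participants may tick that they do not recall a value, so the number analysed could be smaller. The correction is worth making because it costs almost nothing.

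**What to change.** 1. In Monitor trend perception analysis and in Statistical methods, limit Fisher's exact test to the categorical trend outcomes.
2. For the percentage errors in initial, final and change in pressure, name a comparison of the two independent groups defined by which task was performed second. Use an unpaired t-test, or Mann-Whitney if the Shapiro-Wilk test already planned rejects normality. The t-test matches the mean and SD the plan reports. Any two-independent-group method would serve, so Mann-Whitney throughout would be a preference rather than a requirement.
3. In the Introduction, restrict paired t testing to the timing data.

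Cost: wording only. Conduct, randomisation and data collection do not change.

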However there is a key difference in the clinical populations found in the literature, surgeons have an operative team and are not responsible for patient monitoring while operating. Likewise anaesthetists are usually accompanied by an ODP and are not undertaking practical skills in isolation.

We were not able to find any published literature addressing attention and perception during ICU procedures.

What does this research add?

There is no published experimental data investigating how clinician time perception and attention are impacted by performing tasks in an IC environment. There is an expectation that time perception and attention are preserved, such that clinicians can insert central access as a sole practitioner. Should our investigation show that attention is impacted then this could inform changes to practice as to how monitors and/or additional staff members are utilised during procedures and clinical tasks and how practitioners are trained to undertake them.

AIM(S) OF STUDY

- To investigate the relationship between task type, perceptual loading and attention in an ICU environment
- To investigate the relationship between task type, perceptual loading and time perception in an ICU environment
- To examine if the extent of these effects (if any) are affected by clinician role and/or experience

OBJECTIVES

The objective of this study is to measure clinician awareness of time progression and monitoring trends in the clinical environment during 2 different types of task.

HYPOTHESIS

H₀: Task type has no impact on clinician time perception or awareness of monitoring trends.

H_A: In the technical task clinician time awareness is more inaccurate than in the administrative task

H_B: In the technical task clinician awareness of monitoring trends is impaired compared to in the administrative task

STUDY DESIGN

STUDY SETTING/LOCATION

This will be a single-centre study undertaken in the Intensive Care Units at Great Ormond Street Hospital. The study tasks will be run in the simulation room on the general Paediatric ICU.

STUDY POPULATION

Participants will be recruited from the group of ICU junior/senior tier fellows and Consultants working on the ICUs at Great Ormond Street Hospital. This comprises a pool of around 40 staff members. All staff members are routinely involved in the care of patients in a PIC environment.

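### The timing hypothesis is about inaccuracy against a 10-second target, but the planned t-tests compare the intervals themselves and never their distance from 10 s

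*Combined protocol and SAP*

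**What the plan says.** The Hypothesis section states H_A as "In the technical task clinician time awareness is more inaccurate than in the administrative task". The only standard set for the pedal data is in the task instructions: "Please press the foot pedal every 10 seconds, trying to be as accurate as possible". The Introduction gives the purpose of the tests: "Analysis will involve paired t testing of the timing interval and observation trend data to see if task loading significantly impacts accuracy".

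The quantities derived and tested are these:

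- **Primary Outcomes:** "Mean and standard deviation (accuracy) of time intervals measured".
- **Time interval analysis, derived values:** the minimum, maximum, mean, interquartile range and SD of the intervals in each scenario.
- **Time interval analysis, comparisons with the control task:** "Mean deviation for each individual from their baseline in each of the tasks" and "Overall proportion of participants showing significant deviation from their own baseline in each of the administrative and technical tasks".
- **Time interval analysis, recalled total time:** a comparison with the true total, "Reported as percentage error of actual elapsed time".
- **Statistical methods:** "With assumed normally distributed timing data and each participant completing 2 tasks the distributions will be compared with a paired sample t-test for" three pairs: control with administrative, control with technical, and administrative with technical.

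No distance of an interval from 10 s, whether signed, absolute or squared, is derived anywhere.

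**The concern.** A paired t-test on intervals asks whether the average pace differs between tasks. H_A asks whether participants are further from the target in one task than in the other. Someone who speeds up and someone who slows down are both less accurate, but in a mean of signed differences they cancel.

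The other planned timing outputs do not fill the gap:

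- The SD, which the plan labels as accuracy, measures consistency. A steady press every 7 s has an SD near zero and is 3 s wrong each time.
- Deviation from the participant's own control pace is not deviation from 10 s, because the control pace may itself be off.
- The proportion deviating significantly can count both directions, but it uses the same own-pace reference and has no named test between tasks.
- The percentage error for recalled time is a different measure, and it is not said to be signed or absolute.

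A null interval test could therefore sit beside a real loss of accuracy, and a significant one would not say which task is worse. The Outcomes and Significance section says that significant impairment of time perception in a technical procedure would point to the need for an assistant and to policy changes. The tested quantity should therefore measure impairment.

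**Working it through.** **Inputs from the documents.** The target is 10 s, tasks last up to 6 minutes, and the staff pool is about 40. There is no sample size, SD, alpha or expected shift, so there is no plan figure to reproduce.

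**Algebra.** Let A and T be a participant's mean interval in the administrative and technical tasks.

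- Planned contrast: mean(T − A).
- Contrast that H_A needs: mean(|T − 10| − |A − 10|).

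The two are equal if every A and T is at or above 10 s. If all are at or below 10 s, they have opposite signs. Otherwise they can differ by any amount. For example, take four participants with A = 10 s and T = 7, 13, 7 and 13 s. The planned contrast is (−3 + 3 − 3 + 3)/4 = 0. The accuracy contrast is (3 + 3 + 3 + 3)/4 = 3 s.

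**Simulation assumptions (mine).** n = 10, 20 or 40; 36 presses per task (360 s / 10 s); correlation 0.5 between a participant's paces in the two tasks; two-sided 0.05; press-to-press SD w equal in both tasks; 4,000 simulated studies per case. The accuracy test is a paired t-test on each participant's mean |interval − 10|.

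*Case 1: paces centred on 10 s, between-participant SD 1 s (administrative) and 2 s (technical).* The expected absolute error is √(2/π) × √(s² + w²). At w = 2 this is 0.798 × √5 = 1.78 s and 0.798 × √8 = 2.26 s.

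| w | Interval test, any n | Test on SDs, any n | Absolute-error test, n = 10 / 20 / 40 |
|---|---|---|---|
| 1 s | about 5% | about 5% | 39 / 82 / 99% |
| 2 s | about 5% | about 5% | 30 / 72 / 97% |
| 3 s | about 5% | about 5% | 21 / 51 / 86% |

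With a smaller gap (SD 1 s against 1.5 s) at n = 20, the absolute-error test rejects 41/29/17% for w = 1/2/3 s, and the interval test still about 5%.

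*Case 2: administrative 8 s, technical 10 s, between-participant SD 1 s in both.* The interval test rejects in 99.6 to 100% of studies, although the technical task is the more accurate. At n = 20 the absolute-error test favours the technical task in 99/97/86% for w = 1/2/3 s.

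*Case 3: average error +0.5 s (administrative) and +2 s (technical), between-participant SD 1.5 s, w = 2 s, so errors are mainly long.* The interval test is the better one: 77/98/100% against 34/68/94% for absolute error at n = 10/20/40.

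*No difference between tasks (SD 1.5 s in both, n = 20, w = 2 s).* The interval test rejects 5.0% and the absolute-error test 4.5%, so both hold their level.

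**Own-pace proportion.** The plan names no test for this use, so I assumed a two-sample t-test of 36 control against 36 task intervals per participant. A participant at 8 s in both control and task, 2 s off target, is flagged 5% of the time. A participant at 8 s in control and exactly 10 s in the task is flagged 100/99/80% of the time for w = 1/2/3 s.

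**The case against.** The strongest reply has five parts.

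1. **Case 1 depends on equal press-to-press SD.** This is correct. If that SD also rises from 2 to 2.5 s in the technical task, a paired test on SDs rejects about 96% at n = 10 and 100% at n = 20, against 88% and almost 100% for absolute error. But the plan names no t-test on SDs, and such a test would show loss of consistency, not distance from the target.
2. **Descriptive outputs would show the problem.** In part they would. Population limits would widen in case 1. With control SD 1 s and correlations of 0.5, the proportion deviating from own pace would rise from 40% to 60% at w = 2 s. In case 2 the reported means of 8 s and 10 s show which task is off. These help a careful reader, but none is a test of H_A.
3. **The participant's own baseline is a deliberate reference, and H_A does not name 10 s.** Both are true. A control comparison is useful for change in pace. It measures accuracy only if the control pace is itself accurate, which the plan does not assume.
4. **The direction is known.** The Background cites literature that prospective timing overestimates, more so under load. That would favour the signed test, as in case 3. The plan does not adopt it as an assumption.
5. **It is a hypothesis-generating pilot.** This lowers the consequence. It does not align the test with the hypothesis.

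The choice of accuracy measure is also open. Mean |interval − 10| mixes bias with press variability. In case 1 at w = 3 s and n = 20 it rejects 51%, against about 71% for |mean interval − 10|.

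**Conclusion.** The concern holds. The planned comparison suits H0 and shows the direction of any change in pace, but it does not by itself test H_A. It does so only when errors run mainly to one known side of 10 s. Outside that condition it can miss a loss of accuracy (about 5% rejection against 72% at n = 20 in case 1 with w = 2 s) or reject strongly when accuracy has improved (case 2). The algebra needs no assumptions. The percentages rest on assumed sample sizes, SDs, correlation and, for case 1, equal press-to-press SD. Because this is a pilot and the timestamps are recorded, the point should be fixed before analysis but does not threaten the study.

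**What to change.** - For each participant and task, compute the mean of |interval − 10 s|. Make technical minus administrative on this quantity the test of H_A, by paired t-test, or by signed-rank test or on the log scale if skewed. |Mean interval − 10 s| is a reasonable alternative if the authors want bias without press variability. The choice should be fixed in advance.
- Keep the interval comparison for H0 and for direction of bias.
- Report the SD as consistency, not accuracy.
- For recalled elapsed time, use absolute percentage error as the accuracy measure.
- If the authors expect errors in one direction only and prefer the signed test for H_A, state that assumption and check it in the data.

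The cost is protocol wording and one derived column, with no new data or procedures. The downsides are skewed absolute errors and less power when errors run mainly one way (68% against 98% at n = 20 in case 3), which is why the signed comparison should stay beside it.
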